## 1.6 STATISTICAL MODIFICATIONS MADE IN THE STATISTICAL ANALYSIS PLAN

The statistical analysis plan history table below gives the timing, rationale, and key details for major changes to the statistical analysis features in the statistical analysis plan. Changes also incorporated in a protocol amendment are cross-referenced to [Table 1](#).

**Table 2 - Statistical analysis plan statistical changes**

SAP version number	Date approved	Rationale	Description of statistical changes
1	This version	
Increased urinary free-cortisol level was observed in animal studies of SAR425899 but the relevance of this finding to human is unclear. The FDA requested to add the measurement of urinary free-cortisol and creatinine from 24h urines at baseline and end of treatment in order to assess the increase in urinary free-cortisol in humans which may suggest a potential effect of SAR425899 on the hypothalamic-pituitaryadrenal axis.
 
In phase I studies an increase of ketones bodies was observed for the SAR425899 high dose group (up to 0.18 mg) but not for placebo and the SAR425899 low dose group. In view of the currently requested administration of up to 0.20 mg of SAR425899 and the potential gastrointestinal side effects together with the simultaneous administration of metformin, the BfArM recommended to consider metabolic acidosis as an adverse event of special interest with an immediate notification in order to recognize this state very early in the study and to discontinue the administration of metformin when applicable.
 
Leptin and microRNA were initially considered as biomarkers of interest in this study. Leptin plasma concentrations are correlated with fat mass. MicroRNA is a surrogate biomarker for nonalcoholic steatohepatitis (NASH). Thus assessment of these two biomarkers was expected to provide information about SAR425899 effect on fat mass and NASH. However the sponsor decided to not measure these parameters anymore during this phase II study. For Leptin, it is not required for any modeling and is not recommended as a surrogate to test for differences in energy expenditure. Nevertheless Leptin and fat mass changes are planned to be assessed in a study dedicated to energy expenditure assessment. For MicroRNA, patients included in this study are not diagnosed for NASH and no liver biopsy is taken which could make the interpretation of microRNA results difficult. Nevertheless microRNA is planned to be assessed in a study dedicated to NASH.
 
Potentially an interim analysis for population PK and PK/PD will be performed for 60% completers, in order to have data for internal project planning purposes.
 
To add Amylase/lipase assessment in Visits 9 and 11 as requested by the BfArM.
 
To change the reference timepoint for blood sampling during the meal test from the end of the standardized meal to the start of the standardized meal and change the time period for the standardized meal consumption from 15 minutes to 10 minutes.
	
Urinary free-cortisol and creatinine measured in 24 hours urines, and the cortisol/creatinine ratio were added to the list of laboratory variables for statistical analyses.
 
Metabolic acidosis was added to the list of AESI parameters for statistical analyses.
 
Leptin and microRNA were removed from the list of pharmacodynamics biomarkers for statistical analyses.
 
An interim PK/PD analysis will be performed for 60% completers.
 
Visit 9 and 11 amylase/lipase assessments will be included in the analyses of amylase/lipase.
 
There will be no change to the planned by timepoint analyses on meal test related efficacy parameters due to the change, however, sensitivity analyses may be performed as necessary.


SAP version number	Date approved	Rationale	Description of statistical changes
1	This version	To be consistent with company standard.	The definition of treatment compliance was changed, with above-planned dosing defined as any day that the patient took a higher dose than planned, and under-planned dosing defined as any day that the patient took a lower dose than planned.
1	This version	Trend tests on HbA1c will be performed instead pairwise comparison of each dose of SAR425899 versus placebo for primary analysis. Same changes are also made for body weight analyses. The hierarchical testing procedure is also updated to reflect the changes.	Trend tests on HbA1c will be performed instead pairwise comparison of each dose of SAR425899 versus placebo for primary analysis. Same changes are also made for body weight analyses. The hierarchical testing procedure is also updated to reflect the changes. Details of the trend tests and hierarchical testing procedure are presented in Section 2.4.4 .
1	This version	Unblinded analyses results on body weight, HbA1c and FPG, and unblinded DMC results (including demographics, disposition, and safety summary) and additional related exploratory analyses will/may be provided to Sanofi internal project planning personnel to support compound development during the 2 interim analyses of the study.	Unblinded analyses results on body weight, HbA1c and FPG, and unblinded DMC results (including demographics, disposition, and safety summary) and additional related exploratory analyses will/may be provided to Sanofi internal project planning personnel to support compound development during the 2 interim analyses of the study. Details are presented in Section 3 .
1	This version	To account for the situation that a patient took a SAR425899/placebo dose level that is different from the planned 4 doses levels allow for the study, specify that if a patient is exposed to more than one dose level of SAR425899 since Week 8 visit or later, then the patient will be analyzed in the dose level administered on Week 8 visit or study Day 56 if Week 8 visit is not available.	Patients will be analyzed for safety analyses according to the treatment actually received. If a patient is exposed to more than one dose level of SAR425899 since Week 8 visit or later, then the patient will be analyzed in the dose level administered on Week 8 visit or study Day 56 if Week 8 visit is not available.

## 2 STATISTICAL AND ANALYTICAL PROCEDURES

### 2.1 ANALYSIS ENDPOINTS

#### 2.1.1 Demographic and baseline characteristics

The baseline value is defined as the last available value before the first injection of investigational medicinal product (IMP) or the last available value on or before the date of randomization if not treated with IMP.

Baseline safety and efficacy parameters are presented along with the summary statistics for safety and efficacy sections ([Section 2.4.5](#) and [Section 2.4.4](#)).

##### *Demographic characteristics*

- Demographic characteristics to be summarized are:
- Age (years) derived as:  $(\text{Date of informed consent} - \text{Date of birth})/365.25$ ;
- Age categories ( $<50$ ,  $\geq 50$  to  $<65$ ,  $\geq 65$  to  $<75$ ,  $\geq 75$  years of age);
- Gender (Male, Female);
- Race (American Indian or Alaska Native, Asian/Oriental, Black, Native Hawaiian or Other Pacific Islander, White, Other);
- Ethnicity (Hispanic or Latino, Not Hispanic or Latino, Unknown);
- Screening (V1) HbA1c (%);
- Randomization strata (V1 screening) of HbA1c ( $<8\%$ ,  $\geq 8\%$ );
- Baseline BMI ( $\text{kg/m}^2$ ) derived as:  $(\text{Weight in kg})/(\text{Height in meters})^2$ ;
- Randomization strata of baseline BMI level ( $<35 \text{ kg/m}^2$ ,  $\geq 35 \text{ kg/m}^2$ );
- Country.

##### *Disease characteristics at screening or baseline*

Disease history includes:

- Duration of diabetes (years) derived as:  $(\text{Date of informed consent} - \text{Date of diagnosis of diabetes} + 1)/365.25$ ;
- Categorized duration of diabetes (years) ( $<10$  years,  $\geq 10$  years)
- Age at onset of diabetes (years) derived as:  $(\text{Date of diagnosis of diabetes} - \text{Date of birth} + 1)/365.25$ ;
- Anti-Hyperglycemic Therapy Categories (Metformin only, Diet/Exercise only, Metformin and diet/exercise)
- Duration of metformin treatment (years) derived as:  $(\text{Date of informed consent} - \text{Date of first dose of metformin} + 1)/365.25$ ;

- Daily dose of metformin at baseline (mg) for patients taking metformin, defined as the last total daily value of metformin intake before the first dose injection of IP for those taking metformin at baseline;
- Categorized daily dose of metformin at baseline (<1500, ≥1500 to <2500, ≥2500 to <3000, ≥3000 mg);
- Baseline diabetic microvascular complications (Yes, No) (ie, diabetic retinopathy, diabetic neuropathy, and diabetic nephropathy);
- History of gestational diabetes (yes or no);
- Baseline urine albumin/creatinine ratio categories (<30 µg/mg [Normal], ≥30 to <300 µg/mg [Microalbuminuria], and ≥300 µg/mg [Macroalbuminuria]);
- Estimated Glomerular Filtration Rate (eGFR) at screening (ml/min);
- eGFR categories at screening (<15 mL/min [End stage renal disease], ≥15 to <30 mL/min [Severe decrease in GFR], ≥30 to <60 mL/min [Moderate decrease in GFR], ≥60 to <90 mL/min [Mild decrease in GFR], and ≥90 mL/min [Normal]).

### ***Medical or surgical history***

Medical history and medical findings include:

- Physical examination;
- Medical or surgical history;
- Alcohol habits;
- Tobacco smoking habits.

Medical and surgical history will be coded to a “lower level term (LLT)”, “preferred term (PT)”, “high level term (HLT)”, “high level group term (HLGT)”, and associated primary “system organ class (SOC)” using the version of Medical Dictionary for Regulatory Activities (MedDRA) currently in effect at Sanofi at the time of database lock.

### **2.1.2 Prior or concomitant medications**

All medications taken within 3 months prior to the screening visit or during study are to be reported in the electronic case report form (eCRF) pages.

All medications will be coded using the version of World Health Organization-Drug Dictionary (WHO-DD) currently in effect at Sanofi at the time of database lock.

Medications will be classified into the following 3 groups:

- Prior medications are those the patient took prior to the first injection of study IMP. Prior medications can be discontinued before first IMP injection or can be ongoing during treatment period.
- Concomitant medications are those the patient continued or started on or after the first injection of study IMP up to 3 days after the last injection of study IMP.
- Post-treatment medications are those the patient continued or started on or after 4 days after the last injection of study IMP.

A given medication can be classified in several groups.

Any technical details related to computation, dates, imputation for missing dates are described in [Section 2.5](#).

### **2.1.2.1 Concomitant diabetes therapy**

Patients can be enrolled with a background therapy metformin. Metformin should be administered according to its locally approved label and should be kept at stable dose throughout the study (same dose as used prior to the study) unless there is a specific safety issue related to this medication.

### **2.1.2.2 Rescue therapy**

In case of fasting plasma glucose (FPG) or HbA1c above pre-defined thresholds and if no reasons can be found for insufficient glucose control, it is recommended to add rescue therapy.

Central laboratory alerts on FPG and HbA1c are set up to ensure that glycemic parameters remain under predefined threshold values (see hereinafter).

The threshold values are defined as follows, depending on study period:

From baseline Visit 4 (Week 0) to Visit 9 (Week 8, including value at Visit 9): FPG >270 mg/dL (15.0 mmol/L).

From Visit 9 (Week 8) to Visit 10 (Week 14): FPG > 240 mg/dL (13.3 mmol/L).

From Visit 10 (Week 14) to Visit 12 (Week 26): FPG>200 mg/dL (11.1 mmol/L) or HbA1c >8%.

In case of FPG / HbA1c above the threshold values, the investigator should ensure that no reasonable explanation exists for insufficient glucose control, and in particular that:

- Plasma glucose was actually measured in fasting condition (ie, after at least 8 hrs fast).
- Investigational product is given at planned dose.
- There is no intercurrent disease, which may jeopardize glycemic control (eg, infectious disease).
- Compliance with treatment is appropriate.
- Compliance with diet and lifestyle is appropriate.

If any of the above can reasonably explain the insufficient glycemic control, the investigator should undertake appropriate action, ie,

- Dose increase of investigational product according to protocol (if tolerance allows).
- Set up adequate investigation and treatment of intercurrent disease (to be reported in AE/concomitant medication parts of the eCRF).
- Stress on the absolute need to be compliant with treatment.

- Organize a specific interview with a Registered Dietician or other qualified nutrition professional and stress on the absolute need to be compliant to diet and lifestyle recommendations, and check a FPG / HbA1c assessment at the next visit.

If none from the above-mentioned reasons can be found, or if appropriate action fails to decrease FPG / HbA1c under the threshold values, rescue medication may be introduced.

The choice of rescue therapy is at the investigator's discretion with the exception of using GLP-1 receptor agonists or DPP4 inhibitors.

### **2.1.2.3 Prohibited concomitant therapy**

Use of the following medications will not be permitted during the study:

- Weight control treatment, including any medication with a labelled reference to weight loss or weight gain.
- Systemic glucocorticoid use for more than 7 days.
- Any antidiabetic treatment other than IMP, authorized background antidiabetic therapy and rescue therapy, if necessary.
- GLP-1 receptor agonists or dipeptidyl peptidase 4 (DPP4) inhibitors.
- Drugs that affect gastrointestinal motility (eg, chronic use of anticholinergics, antispasmodics, 5HT3 antagonists, opiates).
- Medications that may cause significant weight gain such as antipsychotic medications, tricyclic antidepressants, and mood stabilizers (eg, imipramine, amitriptyline, mirtazapine, paroxetine, phenelzine, chlorpromazine, thioridazine, clozapine, olanzapine, valproic acid and its derivatives, and lithium), and growth hormone.
- Cannabis, even if prescribed for medical reasons.

Any technical details related to computation, dates, imputation for missing dates are described in [Section 2.5](#).

### **2.1.3 Efficacy endpoints**

All biological efficacy assessments will be performed by a central laboratory. All scheduled measurements collected during the study will be used in the analysis, including those obtained after IMP discontinuation or rescue medication use.

Efficacy variables will be summarized in both standard international units and conventional units when applicable.

The baseline value for efficacy endpoints is the last available value prior to the first injection of IMP or the last available value on or before the date of randomization if not treated with IMP.

HbA1c is assayed at screening (Visit 1); at Visit 4 (Day 1) before first IP injection; at Visit 6 (Week 2); at Visit 8 (Week 4); at Visit 9 (Week 8); at Visit 10 (Week 14); at Visit 11 (Week 20); and at final assessment (Visit 12 at Week 26, primary endpoint assessment visit).

Body weight is measured at screening (Visit 1); at Visit 4 (Day 1) before first IP injection; at Visit 6 (Week 2); at Visit 8 (Week 4); at Visit 9 (Week 8); at Visit 10 (Week 14); at Visit 11 (Week 20); and at final assessment (Visit 12 at Week 26, primary endpoint assessment visit).

FPG is measured at a central laboratory at screening (Visit 1); at Visit 4 (Day 1) before first IP injection; at Visit 6 (Week 2); at Visit 8 (Week 4); at Visit 9 (Week 8); at Visit 10 (Week 14); at Visit 11 (Week 20); and at final assessment (Visit 12 at Week 26, primary endpoint assessment visit).

The self-monitored plasma glucose (SMPG) is measured over a single 24-hr period in the week before Visit 4 (Day 1) before first IP injection, Visit 10 (Week 14), and Visit 12 (Week 26, primary endpoint assessment visit).

Fasting insulin are measured at Visit 4 (Day 1) before first IP injection; at Visit 10 (Week 14); and at final assessment (Visit 12 at Week 26, primary endpoint assessment visit).

Following list of standardized meal test related measurements at premeal, 10 min, 20 min, 0.5 h, 1 h, 1.5 h, 2 h, 3 h, 4 h post meal at Visit 3 (Week -1); and at final assessment (Visit 12 at Week 26, primary endpoint assessment visit) in up to 50% subset of all patients:

- post-prandial plasma glucose (PPG) and associated glucose excursion
- postprandial insulin, proinsulin and C-peptide and associated excursion values

Pre-meal measurements of pro-insulin and C-peptide from the meal test will be used as fasting pro-insulin, and C-peptide values.

The variables HOMA-IR (homeostasis model assessment for insulin resistance) index and HOMA- $\beta$  (homeostasis model assessment for  $\beta$ -cell function) index, derived from fasting plasma glucose and fasting plasma insulin (FPI), are calculated as:

$$\text{HOMA-IR index} = [\text{FPI } (\mu\text{U/mL}) \times \text{FPG (mmol/L)}] / 22.5,$$

$$\text{HOMA-}\beta \text{ index} = ([20 \times \text{FPI } (\mu\text{U/mL})] / [\text{FPG (mmol/L)} - 3.5]).$$

HOMA-IR and HOMA- $\beta$  will be derived at Visit 4 (Day 1) before first IP injection; at Visit 10 (Week 14); and at final assessment (Visit 12 at Week 26, primary endpoint assessment visit).

Fasting lipid profile (total cholesterol, triglycerides, LDL-C, and HDL-C) and free fatty acids will be assessed at screening, Visit 4 (Day 1) before first IP injection; at Visit 10 (Week 14); and at final assessment (Visit 12 at Week 26, primary endpoint assessment visit).

Ketone bodies is assessed at Visit 4 (Day 1) before first IP injection; at Visit 8 (Week 4); at Visit 9 (Week 8); at Visit 10 (Week 14); at Visit 11 (Week 20); and at final assessment (Visit 12 at Week 26, primary endpoint assessment visit).

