- ^a In case of rescue therapy, all assessments planned in V12 should be performed before starting rescue therapy, patients then continue the study treatment (including metformin), and all visits and assessments should be performed as scheduled. In case of premature permanent IMP discontinuation, patients should have a visit as soon as possible with the assessments normally planned in V12 (the standardized meal test and PK collections are performed only if the patient receives the IMP the day of the visit, note that otherwise predose PK sample can be taken if the patient receives the IMP the day before). Afterward, the patients should continue in the study up to the scheduled date of study completion. They should be followed up according to the study procedures as specified in the protocol (except for the 3 day safety post-treatment and PK assessment). If the patient drops out from the study at the time of IMP discontinuation regardless if the patient receives the IMP or not on the day of the meal test, the meal test should be performed. However, PK collections are performed only if the patient receives the IMP the day of the visit, otherwise predose PK sample can be taken if the patient receives the IMP the day before.
- ^b Weight will be recorded to the nearest 0.1 kg and should be measured using calibrated scales. The same pair of scales should preferably be used throughout the trial. Weight should be measured in the fasting state in the morning at approximately the same time with an empty bladder, without shoes and only wearing undergarments or light clothing. Weight measured at screening Visit 1 will be used only for calculation of screening BMI for eligibility criteria whereas weight measured at Visit 4 will be used as baseline for assessment of change in body weight and for calculation of baseline BMI which will be the BMI value used for stratification.

- c* At Visit 9, abbreviated/targeted physical examination only.
- d* Diary will be reviewed at each on site visit.
- e* Counseling will be provided at screening Visit 3 or Visit 4.
- f* Only for patients in SAR425899 or Placebo arms.
- g* First dose of IMP will be done on-site .IMP administration every day along the 26-weeks, but at each visit on site, the IMP administration will be done on site by the patient himself.
- h* 7-point profile to be conducted over a single 24-hour period in the week before Visit 4, Visit 10 and Visit 12.

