9.2.1.2.2 Standardized meal test definition and change in postprandial glucose

Patients will undergo a standardized meal challenge to assess PPG, insulin, proinsulin, C-peptide as well as excursion values for above parameters at Visit 3 (Week -1) and at the end of treatment (Visit 12, Week 26) ([Table 2](#)).

A standardized meal will be served 2 hours after morning dose (at T2H) on Visit 12 (Week 26), and at the corresponding time on Visit 3 (Week -1). The standardized meal for all patients should be consumed within a 10-minute period.

The standardized meal contains approximately 600 kcal and is composed of 50 to 55% carbohydrates, 15 to 20% proteins, and 25 to 30% fat. The composition and quantity of standardized meal must be identical throughout the study.

The start of the standardized meal is defined as a reference timepoint for further blood sample collection.

Blood samples for determination of plasma glucose, and insulin, proinsulin, C-peptide, in response to meal test will be collected at (premeal, 10 min, 20min, 0.5h, 1h, 1.5h, 2h, 3h, 4h postmeal) on Weeks -1 and 26. The excursions values for plasma glucose, and insulin, proinsulin, C-peptide will be calculated by subtracting the premeal values from the values collected for each respected timepoints at 10min, 20min, 0.5h, 1h, 1.5h, 2h, 3h and 4h. The AUC values for the above meal test parameters may be calculated as necessary.

Meal test ingestion time should be recorded in the eCRF.

Meal test will be proposed to all the population, and will be limited to the first up to 50% of patient who agree.

If the patient needs to receive a rescue antidiabetic medication, the standardized meal test should be performed before the introduction of the rescue medication and at the end of the study.

In case of permanent discontinuation of the treatment with IMP, the standardized meal test should be performed only if the patient receives the IMP on the day of the visit. The meal test should also be performed at the end of study as planned.

Table 2 - Sampling schedule for glucose, insulin, proinsulin and C peptide in response to a standardized meal test in up to 50% subset of all patients

Blood sampling time (hh:mm)	Blood sampling
Morning study treatment injection	00:00
Pre meal	X
Standardized meal	02:00
2h10 after morning injection	02:10
2h20 after morning injection	02:20
2h 30 after morning injection	02:30
3h00 after morning injection	03:00
3h30 after morning injection	03:30

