10 STUDY PROCEDURES

10.1 VISIT SCHEDULE

The visit schedule and procedures/assessments listed in the study flow chart in [Section 1.2](#) are not repeated in this section.

The aim of this section is to provide details on how some of the procedures/assessments have to be performed.

The study consists of 10 on-site visits and 3 phone-call visits.

The patient has to be fasting for all on-site visits. For all these visits, the patient should be seen in the morning, at approximately the same time, as far as possible.

The fasting condition is defined as an overnight fast no less than 8 hours that consisted of no food or liquid intake, other than water. The IMP and other glucose-lowering agents (ie, metformin) should be administered after the fasting blood sample is drawn for all laboratory tests on the study site.

Note: If the patient is not fasting at the visits specified above, the blood sample will not be collected and a new appointment should be given to the patient for the following day if possible, with instruction to be fasted.

Visit window: during the screening period and for randomization visit a visit window of ± 3 days is acceptable. During the treatment period a visit window of ± 3 days is acceptable between Visit 4 (Week 0) and Visit 9 (Week 8), and a visit window of ± 5 days is acceptable from Visit 10 (Week 14) to Visit 12 (Week 26). A visit window of -1 days or +3 days for the post-treatment follow up visit (V13) is acceptable using the day of V12 as reference. If one visit date is changed, the next visit should occur according to the original schedule.

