10.1.2.1.8 End of treatment Visit 12 (Week 26)

The patient should return to the investigational site in the morning in fasting condition (at least 8 hours fasting) with the study medication box containing used and unused cartridges, pen device, glucometer and the diary.

The visit includes:

- Recording of AEs.
- Recording of hypoglycemic events (if any).
- IRT contact.
- Recording of the use or change of any concomitant medications.
- Review of the patient's diary, compliance with study medication and use of the glucometer.
- Vital signs.
- Body weight.
- Physical examination.
- 7-point glucose profile to be conducted on the day prior to visit beginning in the morning.
- 12-lead ECG.
- Holter monitor if applicable (subset of patients).
- Standardized meal test with VAS for appetite/satiety in a subset of patients (see [Section 9.2.1.2.2](#) and [Section 9.2.1.2.7](#)).
- Waist and hip measurements.
- Laboratory assessments performed by the central laboratory:
 - HbA1c,
 - FPG,
 - Fasting insulin for calculation of HOMA- β , HOMA-IR,
 - Pregnancy test,
 - Clinical chemistry and hematology,
 - Lipid panel,

- Ketone bodies,
- Fasting level of adiponectin,
- Amylase/lipase,
- Calcitonin,
- TSH/T3/FT4
- Urinalysis,
- Anti-SAR425899 antibodies,
- Urinary free-cortisol and creatinine measured in 24 hours urines.

PK sampling will be collected (sparse or full if applicable) ([Section 9.3.1.1](#)).

PRO questionnaires and PRO qualitative questions will be completed by the patient.

Exploratory biomarkers.

The patient is instructed, in case of occurrence of AE, to contact /return to the site as deemed appropriate.

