### **2.1.3.2 Secondary efficacy endpoint(s)**

#### **Continuous secondary efficacy endpoints**

The continuous secondary efficacy endpoints are:

- Change in body weight from baseline to Week 26,
- Change in FPG from baseline to Week 26,
- Change in 7-point SMPG profiles from baseline to Week 26 (each time point and average daily value),
- Change in PPG and in blood glucose excursion in response to a standardized meal test in up to 50% subset of all patients from baseline to Week 26 at time points premeal, 10 min, 20 min, 0.5 h, 1 h, 1.5 h, 2 h, 3 h, 4 h post meal,
- Change in fasting insulin, proinsulin, and C-peptide from baseline to Week 26,
- Change in insulin, proinsulin, and C-peptide and associated excursion values in response to a standardized meal test in up to 50% subset of all patients from baseline to Week 26 at time points premeal, 10 min, 20 min, 0.5 h, 1 h, 1.5 h, 2 h, 3 h, 4 h post meal,
- Change in HOMA- $\beta$  and HOMA-IR from baseline to Week 26,
- Change in lipid profile (total cholesterol, triglycerides, LDL-C, and HDL-C) and free fatty acids, and Ketone bodies from baseline to Week 26,

For 7-point SMPG profiles, the mean daily (ie, average on 7 points) change from baseline to Week 26 will be analyzed. In addition, the change from baseline to Week 26 for each of the 7 points will be evaluated, respectively.

For FPG, only values assessed in fasting condition will be analyzed.

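### At Week 26 the SAP's 'fasting' proinsulin and C-peptide come from a pre-meal sample that the schedule places after the morning injection, so they should not be labelled or read as fasting values

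*SAP*

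**What the plan says.** The SAP's list of continuous secondary endpoints includes "Change in fasting insulin, proinsulin, and C-peptide from baseline to Week 26". SAP 2.1.3 then gives the source for two of the three analytes: "Pre-meal measurements of pro-insulin and C-peptide from the meal test will be used as fasting pro-insulin, and C-peptide values". Insulin is handled differently. SAP 2.1.3 has it measured at Visits 4, 10 and 12, and the Visit 12 laboratory list in Protocol 10.1.2.1.8 carries it as its own item, "Fasting insulin for calculation of HOMA- β , HOMA-IR". The flow chart has no corresponding fasting line for proinsulin or C-peptide.

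On the meal test, Protocol 9.2.1.2.2 fixes the end-of-treatment timing relative to the injection: "A standardized meal will be served 2 hours after morning dose (at T2H) on Visit 12 (Week 26". The baseline test has no injection to count from, so its meal is matched by clock time instead: "and at the corresponding time on Visit 3 (Week -1". Table 2 in that section counts time from the injection; its first post-meal row reads "2h10 after morning injection". The flow chart note on study drug, attached to Visit 4, says "First dose of IMP will be done on-site", so the Visit 3 meal test precedes any study drug.

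On fasting samples in general, Protocol 10.1 says "The IMP and other glucose-lowering agents (ie, metformin) should be administered after the fasting blood sample is drawn for all laboratory tests".

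**The concern.** One endpoint line names three analytes as if they were sampled under the same condition. Insulin comes from a draw that Protocol 10.1 places before the injection. At Week 26, proinsulin and C-peptide come from a draw that Table 2 places after it.

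The usual reading of a fasting C-peptide or proinsulin change in a 26-week trial is a change in basal beta-cell secretion under continued treatment. A sample taken after that day's injection can also carry a short-term response to the injection. Subtracting placebo does not remove such a response, because placebo patients receive no active drug that morning. A difference could then be reported as basal when part of it is post-dose. It could also be set beside fasting insulin as though the two were comparable.

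**Working it through.** **1. The schedule.** Inputs: meal start 2 h after injection, and meal-relative sampling times of 10, 20, 30, 60, 90, 120, 180 and 240 min (Protocol 9.2.1.2.2). Adding 120 min to each gives 02:10, 02:20, 02:30, 03:00, 03:30, 04:00, 05:00 and 06:00. These match Table 2, so injection = 00:00 and meal = 02:00 is confirmed.

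**2. Where the pre-meal sample falls.** The Table 2 rows run injection, pre-meal sample, meal, post-meal samples. No clock time is printed for the pre-meal row. In the full-PK schedule (Protocol 9.3.1.1, Table 3) the sample labelled pre-dose is listed before the injection row, so the protocol marks a pre-dose sample when it means one. In its Table 2 position the pre-meal sample lies between 0 and 2 h after the injection.

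**3. The analytes side by side.**

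| | Fasting insulin | 'Fasting' proinsulin and C-peptide |
|---|---|---|
| Baseline | Visit 4, before first injection | Visit 3 meal test, before any study drug |
| Week 26 | Visit 12 fasting draw, study drug given afterwards | Visit 12 pre-meal draw, listed after the injection |
| Who has it | All patients | Meal-test subset (up to 50%) |

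The SAP also lists proinsulin and C-peptide at the pre-meal time point among the meal-test endpoints. Under SAP 2.1.3 the same measurement is therefore reported twice, once as pre-meal and once as fasting.

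**4. How far exposure could differ from a pre-dose sample (illustration only).** Protocol 9.2.2.1 equates 3 days with about 5 half-lives, so t½ ≈ 72/5 = 14.4 h and k = ln 2/14.4 = 0.0481 per h. Assume one compartment, once-daily dosing and steady state.

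- Fraction of a dose left at 24 h: exp(−24k) = 0.315. Trough in units of one dose: 0.315/(1 − 0.315) = 0.460. exp(−2k) = 0.908.
- If a fraction F of today's dose is in the circulation from the start, concentration at 2 h over trough = (0.460 + F) × 0.908/0.460. This gives 0.91 for F = 0 and 2.88 for F = 1.
- With first-order absorption at rate ka, C(t) ∝ exp(−kt)/(1 − exp(−24k)) − exp(−ka·t)/(1 − exp(−24ka)). The ratio to trough is C(t)/C(24):

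| Assumed absorption half-life | Ratio at 0.5 h | Ratio at 2 h |
|---|---|---|
| 1 h | 1.56 | 2.34 |
| 2 h | 1.27 | 1.80 |
| 4 h | 1.11 | 1.37 |
| 8 h | 1.04 | 1.15 |

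The documents give no absorption rate. These are ratios of drug concentration, not of proinsulin or C-peptide. They show only that exposure just before the meal could be close to trough or more than double it, and that the unstated draw time matters.

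**The case against.** The strongest reply is that this is a labelling matter. The SAP states its derivation openly, and all arms follow the same meal-test schedule. The randomised comparison at that time point is valid for what it measures. The endpoint is secondary, outside the hierarchy, and available only in the meal-test subset. All of that stands. What it does not rescue is the word 'fasting' and the reading as basal secretion.

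A reader might infer more than the documents support:

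- **That the protocol defines fasting as pre-dose.** It does not. Section 10.1 defines fasting as at least 8 hours overnight with nothing but water. The order of sampling and dosing is a separate instruction. Meal-test patients arrive fasting and have no breakfast before the test meal when PK is sampled the same day, so the sample is fasting with respect to food.
- **That the timing is certain.** It rests on the row order of Table 2 and the 2-hour gap. Protocol 8.1.1 puts the injection after the morning blood tests on clinic days, but also ties it to the meal-test time. A draw soon after the injection would carry little same-day effect.
- **That every value is affected.** Placebo patients get no active drug. Patients who stopped study drug but have the end-of-study meal test get no dose that day.
- **That metformin adds to the problem.** Background metformin is to stay stable and the same instruction covers all on-site visits. No difference between baseline and Week 26 is shown.
- **That a baseline one week earlier biases the comparison.** It applies equally to all arms.
- **That the compound is known to raise these analytes at 2 hours.** The protocol introduction attributes glucose-dependent insulin secretion to GLP-1 and describes SAR425899 as a dual GLP-1/glucagon agonist. It gives no post-dose proinsulin or C-peptide data in fasted patients.
- **That a pre-dose sample would be free of drug.** On the half-life above, about 31% of a dose remains at 24 h. A pre-dose value still reflects ongoing treatment, as intended; it leaves out only that morning's injection.

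**Conclusion.** The point holds in limited form. As the documents are written, the Week 26 'fasting' proinsulin and C-peptide values are food-fasting but, by the order of Table 2, post-injection. That conflicts with the sampling order in Protocol 10.1 and does not match fasting insulin in the same endpoint line. In patients given active drug that day, the change versus placebo can include a same-day effect. Neither its size nor its direction can be derived, and the concentration ratios above must not be taken as an effect size.

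The primary HbA1c analysis, the HOMA indices (built from fasting insulin and FPG) and the hierarchical tests of HbA1c and body weight are not affected. The meal-test endpoints are not at fault either, since the pre-meal value is the proper reference for the excursions.

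Importance is between minor and worth correcting before database lock. Confidence is moderate, because the conclusion depends on a pre-meal draw time that the protocol does not state.

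**What to change.** 1. Reconcile Protocol 9.2.1.2.2 (with Table 2), Protocol 10.1 and SAP 2.1.3 by stating whether the Week 26 pre-meal sample is drawn before or after the injection, and at what time. Protocol 9.2.1.2.5 should be included: it refers to C-peptide samples on flow-chart days, while the flow chart lists only fasting insulin.
2. If the sample is post-dose, change SAP 2.1.3 and the endpoint list so that these values are called pre-meal (post-dose at Week 26) and kept as time zero of the meal test. Remove them from the fasting endpoints, and do not interpret them as basal secretion or alongside fasting insulin. Record this in the SAP's table of statistical changes, which does not mention the substitution. The cost is wording only.
3. Where retained or future samples allow, assay proinsulin and C-peptide on the pre-dose fasting draws at Visits 4 and 12 and use those as the fasting values. This means two extra assays on existing draws and no extra visit or venipuncture. It is a laboratory change as well as a SAP change, and coverage may be incomplete: enrolment began in December 2016, before this SAP, and Protocol 9.4 describes storage only for PK and immunogenicity samples.
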